1.2 Current Treatment Options

Despite improved recognition of CHI, there is no satisfactory treatment or cure for this disease. The two most commonly used long-term medications, diazoxide and octreotide, are not Food and Drug Administration (FDA) approved for this condition, and often are ineffective or have intolerable side effects.

Diazoxide is an oral K_{ATP} channel agonist that maintains the beta-cell K_{ATP} channel in the open state. This prevents beta-cell depolarization and thus inhibits insulin secretion. Although it is the preferred and most widely used medical treatment for chronic hyperinsulinemic hypoglycemia, the most common form of CHI results from mutations in the K_{ATP} channel, and so diazoxide is ineffective in this subset of patients. Even in individuals where diazoxide is effective, side effects are frequent and include fluid retention, edema, hypertrichosis, and hirsutism resulting in abnormal facial features in children (Mohamed et al. 2012). Less common side effects include bone marrow suppression, elevation of uric acid, and importantly, pulmonary hypertension, for which the FDA has issued a black box warning (FDA, 2015).

Octreotide or long-acting release (LAR) agents in the same class (lanreotide) are subcutaneous somatostatin analogs, acting to prevent calcium influx and resultant insulin secretion, downstream of the K_{ATP} channel. While somatostatin analogs have

therapeutic potential in diazoxide-unresponsive patients (Buraczewska et al., 2015; Guemes and Hussain, 2015), this class of medications is only modestly effective in some patients, and can lead to tachyphylaxis. Due to the mechanism of action, somatostatin analogs may suppress other hormones including thyroid stimulating hormone and growth hormone, and have the potential to stunt growth when administered to children over long periods of time. Cholestasis and necrotizing enterocolitis are other less common but serious side effects.

In cases of CHI that are unresponsive to medical management with diazoxide or somatostatin analogs, surgical removal of a portion or the entire pancreas is required. In those with focal pancreatic disease, surgical removal of the specific affected area often results in a cure. In those with diffuse pancreatic disease, a near-total pancreatectomy is undertaken, but residual hypoglycemia requiring adjuvant medical management remains in ~50% of patients (Lord and De Leon, 2013).

Despite improved recognition of CHI and early intervention with currently available therapies, persistent hypoglycemia exists and can result in serious neurological and developmental complications, including persistent feeding problems (Banerjee et al., 2016), recurrent seizures, learning disabilities, and focal brain lesions (Avatapalle et al., 2013; Gataullina et al., 2013; de las Heras et al., 2010; Bahi-Buisson et al., 2008; Mazor-Aronovitch et al., 2007). Current medical therapies for conditions of hyperinsulinism are directed at reducing or eliminating insulin production and/or secretion from the beta-cell, however, they achieve sub-optimal glycemic control and/or have undesirable side effects. Thus, there is a significant unmet medical need to develop new therapies aimed at preventing chronic recurrent hypoglycemia in CHI.

1.3 Overview of RZ358

[figure not shown]
[figure not shown]
[figure not shown]
[figure not shown]
Current medical therapies for conditions of hyperinsulinism are directed at reducing or eliminating insulin production and/or secretion from the beta-cell. These current medications, however, achieve sub-optimal glycemic control and/or have undesirable side effects.

Diminution of insulin action at target tissues may represent a novel therapeutic approach for the treatment of conditions associated with hyperinsulinism. RZ358, previously referred to as XOMA-358 or XMetD, is a fully human immunoglobulin G, subclass 2 (IgG2) mAb that binds with high potency and selectivity to an allosteric site on the insulin receptor (INSR), acting as a negative modulator of insulin action on target cells by attenuating both the binding of insulin and its downstream signaling (Corbin et al., 2014; Issafra et al., 2014). This unique mechanism of action confers properties of reversibility and graded activity which are dependent on the extent of insulin elevation. Therefore, RZ358 is ideally suited as a potential therapy for hyperinsulinism, and it is being developed to treat the hypoglycemia associated with diseases such as CHI.

1.4 (b) (4)

[figure not shown]
(b) (4)

[figure not shown]
(b) (4)

(b) (4)

[figure not shown]
1.5 (b) (4)

(b) (4)
(b) (4)

(b) (4)

(b) (4)

1.6 Rationale

There is a significant unmet medical need to develop new therapies aimed at preventing chronic recurrent hypoglycemia in CHI. Current medical therapies for conditions of hyperinsulinism are directed at reducing or eliminating insulin production and/or secretion from the beta-cell; these current medications achieve sub-optimal glycemic control and/or have undesirable side effects (Banerjee et al., 2016; Avatapalle et al., 2013; Gataullina et al., 2013; de las Heras et al., 2010; Bahi-Buisson et al., 2008; Mazor-Aronovitch et al., 2007).

Diminution of insulin action at target tissues may represent a novel therapeutic approach for the treatment of conditions associated with hyperinsulinism. RZ358, previously referred to as XOMA-358 or XMetD, is a fully human immunoglobulin G, subclass 2 (IgG2) mAb that binds with high potency and selectivity to an allosteric site on the insulin receptor (INSR), acting as a negative modulator of insulin action on target cells by attenuating both the binding of insulin and its downstream signaling (Corbin et al., 2014; Issafra et al., 2014). This unique mechanism of action confers properties of reversibility and graded activity which are dependent on the extent of insulin elevation. Therefore, RZ358 is ideally suited as a potential therapy for hyperinsulinism, and it is being developed to treat the hypoglycemia associated with diseases such as CHI. The combined non-clinical and clinical programs conducted to date support continued clinical development of RZ358 for CHI, and the present study represents the progression of the clinical development plan into repeat-dose studies in younger patients with CHI, in a cohort-based dose-escalation manner.

1.7 Risk-Benefit Assessment

[figure not shown]
[figure not shown]
The available information suggests that the present study has a favorable risk-benefit ratio. Previous studies have shown that single-dose administration of RZ358 up to 9 mg/kg, and repeat-dose administration of up to 3 mg/kg weekly for 4 weeks, was generally safe and well tolerated, with evidence of proof-of-mechanism and concept. No experiments have been performed to determine a specific antidote to RZ358 in the setting of an overdose. General supportive measures should be taken as appropriate.

(b) (4)

As of yet there are no identified risks associated with the use of RZ358 in humans. A summary of non-specific and compound-specific potential risks, based on the presumptive mechanism of action and non-clinical safety data, are described subsequently, along with a summary of mitigation strategies that are implemented into clinical studies of RZ358.

1.7.1 (b) (4)

(b) (4)

(b) (4)

(b) (4)

(b) (4)

• (b) (4)

2 STUDY OBJECTIVES AND ENDPOINTS

The objectives of this study are to evaluate the safety, tolerability, PK, PD, and glycemic efficacy of multiple ascending doses of RZ358 over 8 weeks in patients with hyperinsulinemic hypoglycemia due to CHI.

2.1 Primary Endpoints

- Glycemic efficacy of RZ358 as evaluated by the average daily percent time within a glucose target range of 70-180 mg/dL (3.9-10 mmol/L) by CGM;
- Repeat-dose safety and tolerability of RZ358;
- Repeat-dose PK of RZ358.

2.2 Secondary Endpoints

- Average weekly incidence of hypoglycemia (< 70 mg/dL) by self-monitored blood glucose (SMBG)
- Average daily duration (min) and percent time with hypoglycemia at thresholds of <70, <60, and <50 mg/dL (3.9, 3.3, and 2.8 mmol/L, respectively) by CGM;
- Average daily hypoglycemia incidence (event rate) at each of the specified glucose thresholds by CGM;
- Average 8h overnight percent time in glucose target range of 70-180 mg/dL (3.9-10 mmol/L) by CGM;
- Occurrence of hypoglycemia during a 12h fasting challenge.

2.3 Additional (Exploratory) Endpoints

- Average 8h overnight duration (min) and percent time with hypoglycemia at thresholds of <70, <60, and <50 mg/dL (3.9, 3.3, and 2.8 mmol/L, respectively) by CGM;
- Average 8h overnight hypoglycemia incidence (event rate) at each of the specified glucose thresholds by CGM;
- Average daily and 8h overnight area over and under the glucose curve (AUC, AOC) for each of the specified glucose thresholds by CGM;
- Average glucose level between midnight and 8:00 AM (or nearest pre-breakfast time point) by CGM;
- Average weekly hypoglycemia incidence (event rate) at each of the specified glucose thresholds by SMBG;
- IV or enteral nutritional (glucose/dextrose) supplementation;
- Use of SOC or rescue medications for hypoglycemia (dextrose or other);
- Incidence of fasting blood glucose values >200, >250, and >300 mg/dL (>11.1, >13.9, and >16.6 mmol/L, respectively);
- PD Markers of RZ358 activity including fasting levels of glucose, insulin, c-peptide, glucagon, FFAs, and ketones (beta-hydroxybutarate).

3 STUDY DESIGN AND DESCRIPTION

3.1 Overview

This is a Phase 2, multi-center, open-label, multiple ascending dose study to evaluate the safety, tolerability, PK, PD, and glycemic efficacy of RZ358 in patients with hypoglycemia due to CHI. The study will consist of up to 4 dose cohorts, which are to be enrolled independently and conducted sequentially, comprised of 6-8 patients per cohort. Eligible patients will be successively enrolled into the cohort that is open for enrollment at that time, at the lowest dosing cohort that is yet to be filled.

Advancement to subsequent cohorts will not occur until at least 4 patients from the prior cohort have each received at least 4 weeks of study drug (2 bi-weekly doses), without safety concerns. A Dose Escalation Review Committee will assess all available and relevant interim data from each cohort to determine the appropriateness of dose escalation to a new cohort (see [Section 5.1.2](#)).

In Cohorts 1, 2, and 3 the dose amount will be fixed during the entire 8-week Treatment Period, while in Cohort 4 there will be a scheduled bi-weekly dose-titration for the first 4 weeks, followed by a fixed dose amount thereafter for the remaining 4 weeks. The Sponsor may decide to add a cohort to repeat a dose level or to study an additional dose level, but the dose level for any cohort will not exceed the planned dose level for that cohort, as specified in this protocol.

Table 2: Study Design/Cohort Dosing Regimens

Cohort	Dosing (mg/kg)			
	Wk 1	Wk 3	Wk 5	Wk 7
1	3	3	3	3
2	6	6	6	6
3	9	9	9	9
4	3	6	9	9

Following informed consent, patients will complete a Screening Period to determine eligibility. After the preliminary screening assessment, patients who are otherwise eligible will undergo scheduled self-monitoring of blood glucose (SMBG) by point of care (POC) glucometer as well as have a CGM sensor placed according to the instruction manual, for completion of a 10-day outpatient CGM evaluation to assess glycemic eligibility and establish a baseline. [\(b\) \(4\)](#)

patients will use an SMBG for their POC throughout the trial. Patients taking existing and stable doses of SOC medications or nutritional supplementation for CHI at the time of screening should continue the same regimen and doses throughout this period. [\(b\) \(4\)](#)

o meet glycemic qualification criteria, patients must have glucose values <70 mg/dL (3.9 mmol/L) for ≥4% of the overall monitored CGM time with at least 3 severe hypoglycemia events by CGM threshold of <50mg/dL (2.8 mmol/L) during the last 7 days of a 10-day CGM evaluation period AND be experiencing ≥ 3 hypoglycemia events (<70 mg/dL) per week by SMBG and/or

according to the Investigator's evaluation. (b) (4)

During the Screening Period and throughout the study, patients will be requested to follow their usual diet (including enteral feeding, as applicable) and activity level, as evaluated and instructed by qualified study personnel.

At the conclusion of the CGM and glycemic eligibility evaluation, final eligibility will be determined, and fully eligible patients will check in to the inpatient facility on Day -1, to begin the Treatment Period. On Day -1, patients will begin a 12h baseline fasting challenge evaluation, which will conclude prior to Day 1 dosing. Re-screening may be permitted under certain extenuating circumstances (e.g. laboratory outlier suggesting result artifact, insufficient duration of CGM collection), only with pre-approval by the Sponsor.

Beginning at Day 1 of the Treatment Period, patients will receive study drug via IV infusion every 2 weeks over an 8 week total Treatment Period. Thus, patients who complete the entire Treatment Period will receive 4 doses of study drug over a total of 8 weeks (Figure 1). Patients will remain under inpatient observation for at least 48h following dosing on Week 1 and for at least 24h following dosing on Weeks 3, 5, and 7, for completion of PK blood sampling and safety assessments. Throughout the Treatment Period and through post-treatment follow-up Day 42 after the patient's final dose in the study (cumulative study Day 85), glucose levels will be assessed and recorded by CGM. (b) (4)

patients will continue to use an SMBG as their POC throughout the trial.

Throughout the Treatment period and through the End of Treatment visit (EOT) on post-treatment follow-up Day 14 (cumulative study Day 57), SMBG by POC glucometer must be performed at (b) (4)

Otherwise, changes in the dose or regimen of background SOC therapies should not occur, except in the event that hypo- or hyperglycemic rescue criteria are met (see [Section 5.3.1](#)), or changes are deemed medically necessary by the Investigator.

[figure not shown]
(b) (4)

At the conclusion of Week 7 dosing and discharge from the clinic, each patient will complete outpatient follow-up visits at Days 14 (EOT), 28, and 42 (each ± 3 days), and a final End of Study (EOS) follow-up visit on Day 105 (± 3 days), for purposes of evaluating extended PK and safety over a period of 5 half-lives of the study drug.

A detailed description of study procedures and assessments are provided in [Section 6](#) and are outlined in [Appendix 1](#) (Schedule of Assessments).

[figure not shown]
[figure not shown]
[figure not shown]
Figure 1: Study Design

3.2 (b) (4)

(b) (4)

(b) (4)

A large rectangular area of the page is completely redacted with a solid gray color. The text "(b) (4)" is printed in white at the top left corner of this redacted area.

3.3 End of Study Definitions and Study Duration

End of Treatment (EOT) is defined as the time at which a patient has received all 4 doses of study drug over the course of the 8-week Treatment Period AND completed the associated key EOT assessments at Day 14 (EOT).

A patient is considered to have completed the study if he/she has completed all phases of the study including the last (EOS) visit and the last scheduled procedure shown in the Schedule of Assessments ([Appendix 1](#)). The anticipated study duration for each patient is approximately 26 weeks. This includes a Screening Period of approximately 5 weeks, a Treatment Period of approximately 8 weeks, and an additional 13-week Follow-up Period.

The end of the study is defined as the date of the last scheduled procedure shown in the Schedule of Assessments for the last patient in the trial globally ([Appendix 1](#)).

4 SELECTION AND WITHDRAWAL OF STUDY POPULATION

4.1 Study Population

The study population will consist of male and female patients aged ≥ 12 years and ≤ 45 years with clinically diagnosed CHI.

4.2 Number of Sites Planned

This study will be conducted at approximately 15 investigative sites in approximately 10 countries.

4.3 Inclusion Criteria

Patients who meet ALL of the following criteria are eligible to participate in the study.

1. Provide written informed consent and, as applicable, assent, before any study-specific procedures are performed.
2. At Screening, aged ≥ 12 years and ≤ 45 years.
3. An established clinical diagnosis, with or without a genetic diagnosis, of congenital hyperinsulinism.
4. Patient is currently receiving SOC medications (e.g., diazoxide, lanreotide, sirolimus, pasireotide, or octreotide) and/or nutritional supplementation for CHI, with at least 2 months of stable treatment; OR is not on treatment at the time of Screening.
5. Glucose values <70 mg/dL (3.9 mmol/L) for $\geq 4\%$ of the overall monitored CGM time with at least 3 severe hypoglycemia events by CGM threshold of <50 mg/dL (2.8 mmol/L) during the last 7 days of a 10-day Screening CGM evaluation period.

(b) (4)

AND:

Experiencing ≥ 3 hypoglycemia events (<70 mg/dL) per week by SMBG and/or according to the Investigator's evaluation.

6. Hepatic ultrasound at Screening without clinically significant findings, including clinically significant gallstones as judged by the Investigator (e.g. large size, obstructive, biliary colic or LFT abnormalities exceeding protocol thresholds), or evidence of peliosis hepatitis.

7. For female patients of childbearing potential, a negative serum or urine pregnancy test within 7 days before dosing;
 - Females of childbearing potential are defined as fertile following menarche and until becoming postmenopausal or permanently sterile. (Postmenopausal is defined as absence of vaginal bleeding or spotting for at least 1 year. Permanently sterile is defined as having had a hysterectomy, bilateral salpingectomy, or bilateral oophorectomy.)
 8. For female patients of childbearing potential, a willingness to use highly effective* contraceptive measures adequate to prevent a new pregnancy for the duration of the study, including for at least 105 days after receiving the last dose of study drug. For women with reproductive potential who use a hormonal method of contraception, concurrent use of a second (barrier) method is recommended.
- *Highly effective methods of birth control are defined as those that alone or in combination result in a low failure rate (i.e. less than 1% per year) when used consistently and correctly (e.g. implants, injectables, oral contraceptives, some intrauterine devices, bilateral tubal occlusion, true sexual abstinence in line with the preferred and usual lifestyle of the patient, or vasectomized partner).*
9. For sexually active males, a willingness to use contraceptive measures, e.g. a condom, for the duration of the study, including for at least 105 days after receiving the last dose of study drug.

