4.4 Exclusion Criteria

Patients will be excluded from the study if ANY of the following criteria are met:

1. Any out-of-range laboratory value at Screening that has not been reviewed, approved, and documented as not clinically significant by the Investigator, with the exception of liver function tests for total bilirubin, alanine transaminase (ALT), aspartate transaminase (AST), and alkaline phosphatase (ALP), which must be within 1.5X the upper limit of normal (ULN) for the reference range.
2. Body mass index (BMI) $\geq 35 \text{ kg/m}^2$ for patients aged 18 years and above, or BMI $\geq 99\%$ (percentile) per CDC growth charts for patient >12 and <18 years of age.
3. History of malignancy within 3 years before Screening, other than carcinoma in situ of the cervix or adequately treated non-metastatic squamous or basal cell carcinoma of the skin.
4. History of seropositivity for HIV antibody, hepatitis B, or hepatitis C antibody.
5. Major general surgery within 3 months before Screening or anticipated during the study period.

6. Use of systemic corticosteroids within 30 days before Screening.
7. Known allergy or sensitivity to RZ358 or any component of the drug.
8. Treatment with an investigational drug or device within 30 days or 5 half-lives of the investigational drug before Day 1 of Week 1: whichever is longer. Participation in registries and purely diagnostic studies is allowed.
9. Female patients who are pregnant, planning to become pregnant during the course of the study, have recently delivered (within 3 months before Screening), or are breastfeeding.
10. Male patients who are planning a pregnancy with a female partner during the course of the study or within 105 days after administration of study drug.
11. Any organ condition, concomitant disease (e.g. psychiatric illness, severe alcoholism, or drug abuse, cardiac, hepatic, or kidney disease), or other abnormality that itself, or the treatment of which, could interfere with the conduct of the study (e.g. may affect absorption, distribution, metabolism, or elimination of the study drug) or that, in the opinion of the Investigator and/or Sponsor's Medical Monitor would pose an unacceptable risk to the patient in the study.

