6.3.5 Medical History

Medical history will be recorded at Screening and will include full CHI history, clinically significant diseases, surgeries, cancer history, reproductive status or cardiovascular events. At the time of each follow-up physical examination, an interval medical history should be obtained and any changes in medications and allergies should be recorded.

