6.3.14.4 Pregnancy

Pregnant patients will not be allowed to participate in this study. If a patient becomes pregnant while on study, the patient will be discontinued and will complete end of study procedures for safety. The Sponsor must be notified if any patient becomes pregnant either while receiving study drug or within 105 days after having received the last study drug dose. This includes any pregnancies in the partner of a male study patient, or if a patient's sperm is used to impregnate a female during the study. The Investigator must inform the Sponsor as soon as possible and no later than 24 hours after knowing of the pregnancy, by completing the Pregnancy eCRF page. If the site has a temporary interruption in its internet or computer access, the back-up Pregnancy paper form will be completed and e-mailed to the sponsor within 24 hours of awareness. When the eCRF becomes available, the Pregnancy must be entered by the site within 24 hours. Pregnancy should not be recorded on the AE eCRF.

Upon knowledge of a pregnancy, the pregnant female will be asked to sign a release of information form to allow the Investigator to collect information about the pregnancy, delivery, and final outcome, including health of the baby, as required for regulatory reporting purposes. All reported pregnancies (even if a patient withdraws from the study) must be followed up by the Investigator to final outcome, using the pregnancy and pregnancy follow-up forms. Follow-up and outcome, including any premature termination, must be reported to the Sponsor (or designee) in a timely manner. An evaluation after the birth of the child may also be conducted.

Pregnancy itself should not be recorded as an AE, although any complications ensuing from a pregnancy must be recorded as AE(s). If the infant has a congenital anomaly/birth defect this must be reported and followed up as a SAE.

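### Criterion 7 counts any year without bleeding as postmenopausal, so at ages 12–45 criterion 8 does not clearly require contraception from an amenorrhoeic but possibly fertile patient

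*Protocol*

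**What the plan says.** Criterion 7 in Protocol Section 4.3 requires a negative pregnancy test in the week before dosing from females of childbearing potential, and defines that group: "Females of childbearing potential are defined as fertile following menarche and until becoming postmenopausal or permanently sterile". It then defines the two ways out. Permanent sterility is limited to three named surgical procedures. Menopause is defined by time alone: "Postmenopausal is defined as absence of vaginal bleeding or spotting for at least 1 year". The synopsis repeats this wording.

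Criterion 8 has the same scope: "For female patients of childbearing potential, a willingness to use highly effective* contraceptive measures" are required during the study and for at least 105 days after the last dose. Its next sentence recommends adding a barrier method for women with reproductive potential who use a hormonal one. Its footnote lists implants, injectables and oral contraceptives among the acceptable methods, on the basis that they "result in a low failure rate (i.e. less than 1% per year) when used consistently and correctly".

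Criterion 2 sets the age range at 12 to 45 years. The SAP contains no rule on contraception.

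**The concern.** At 12 to 45 years, a year without bleeding does not by itself show that fertility has ended. Illness or low weight can stop menstruation in a patient who may still conceive, or who may become able to conceive again during the study. The definition does not separate that patient from one who has reached menopause, although the sterility definition beside it is tied to specific operations.

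Criterion 8 takes its scope from this definition, so an error in classification passes straight into the contraception rule. What is at stake is an avoidable pregnancy exposed to an investigational antibody. The sponsor evidently wants to prevent this: contraception runs to 105 days after the last dose, exclusion 10 bars men planning a pregnancy within the same interval, and Section 6.3.14.4 requires pregnancies to be reported within 24 hours. About 15 sites in about 10 countries will apply the definition, and they should not have to supply an unwritten condition.

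**Working it through.** The plan gives no figure to reproduce. The check is a trace through the criteria, with one short calculation for size.

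**1. The chain.** Contraception (criterion 8) applies to females of childbearing potential. That status ends at menopause or permanent sterility (criterion 7). Menopause is at least a year without bleeding (criterion 7). No cause, minimum age or hormone level is stated in either place.

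**2. Test case A: amenorrhoea from illness or low weight, no method in use.** The patient is post-menarchal and has not bled for over a year.
- Literal reading: she meets the definition of postmenopausal, leaves the childbearing group, and neither criterion 8 nor the criterion 7 test applies to her.
- Reading led by *fertile*: the governing sentence describes a fertile person who has not yet become postmenopausal. She still fits it, so both criteria apply.

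The text permits both readings. Which one a site adopts decides whether contraception is required.

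**3. Test case B: bleeding suppressed by a hormonal contraceptive.** The literal definition would release her too. However, criterion 8's barrier-method sentence treats users of hormonal contraception as possibly having reproductive potential, which points the other way. While she continues the method, little is at stake:
- Last dose, from Section 3.1: post-treatment Day 42 is cumulative Day 85, so 85 − 42 = day 43. Check: Day 14 is cumulative Day 57, and 57 − 14 = 43.
- End of the contraception period: 43 + 105 = day 148.
- Period from Day 1: 148 − 1 = 147 days, or 21 weeks.
- Failure bound, from the footnote's limit of under 1% per year and assuming a constant rate with consistent use: 1% × 147/365 = 0.40%.

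The material case is therefore A.

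**4. Does other visible text require contraception in case A?**

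| Provision | What it does | Requires contraception? |
|---|---|---|
| Exclusion 9 (Section 4.4): "Female patients who are pregnant, planning to become pregnant during the course of the study" | Bars current or intended pregnancy, recent delivery and breastfeeding | No; an unplanned pregnancy is not covered |
| Exclusion 11 (Section 4.4) | Lets the investigator or Medical Monitor exclude for disease or other abnormality | No; discretionary |
| Section 6.3.5, Medical History | Records reproductive status at Screening | No; may reveal the problem |
| Synopsis, Study Design | Checklist with Medical Monitor approval before cohort placement | No; may reveal the problem |
| Section 6.3.14.4: "If a patient becomes pregnant while on study, the patient will be discontinued and will complete end of study procedures for safety" | Acts for any patient who conceives | No; acts after conception |

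Several of these could catch a misclassified patient. None makes contraception a condition for one who meets the written definition.

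**5. What cannot be checked.** Parts of the risk section (1.7), the laboratory section and the Schedule of Assessments are redacted. They may contain hormone tests, pregnancy tests or contraception instructions.

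**The case against.** The strongest reply is that the literal reading is unnatural. The operative sentence speaks of a fertile person becoming postmenopausal, and the parenthesis can be taken as saying only how long bleeding must have been absent. Few investigators would call an adolescent with low-weight amenorrhoea postmenopausal. This largely stands: it makes the defect an ambiguity. It does not remove it, because the protocol supplies its own definition of the term, and that definition rests on absence of bleeding alone.

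A second reply is that criterion 8 itself treats hormonal users as potentially fertile, so hormonal suppression is a weak example. That also stands, and the point rests on patients using no method.

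A third is that misclassification would have to survive the medical history, the checklist and exclusion 11, and that redacted text may add safeguards. This lowers the likelihood. It does not alter a definition printed in full in two places.

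A fourth is that requiring no alternative cause still leaves unexplained amenorrhoea classed as menopause. That is true of the proposed wording and is taken up under the fix.

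**Conclusion.** The point holds as a wording gap. In a population aged 12–45, the definition read literally releases a possibly fertile, amenorrhoeic patient who uses no method, so criterion 8 does not clearly require contraception from her. It is a low-priority participant-safety improvement, not a statistical error.

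Size: the documents give no count. An affected patient must be female, post-menarchal, without bleeding for a year for a reason other than menopause, still able to conceive, using no method, and classified by the literal reading. Among 24 to 32 patients of both sexes, that is probably very few, and possibly none. Efficacy is unaffected.

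A reader might infer more in four ways that the documents do not support.
- That criterion 8 plainly exempts such a patient, or that criteria 7 and 8 contradict each other. The word *fertile* leaves the contrary reading open.
- That she would go untested for pregnancy. Criterion 7 read literally does not require the test, but the redacted Schedule of Assessments may.
- That women on hormonal contraception are the main group at risk. Criterion 8 points the other way, and the bound of 0.40% over 147 days is small for those who continue consistently.
- That slow elimination, suggested by follow-up "for purposes of evaluating extended PK and safety over a period of 5 half-lives of the study drug", strengthens the case. Drug persisting after discontinuation applies equally to a patient within criterion 8 whose contraception fails, so it says nothing about whether the definition is faulty.

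The conclusion assumes that at least some sites would apply the definition as printed, and that no redacted text adds a condition on cause.

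**What to change.** In criterion 7 of Section 4.3 and in the synopsis, keep the one-year criterion and append: *without an alternative medical cause, including hormonal suppression*. Patients with another cause then stay within childbearing potential, and criteria 7 and 8 apply to them with no further edit.

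The clause does not resolve amenorrhoea that remains unexplained. If the sponsor wants to cover that as well, hormonal confirmation of menopause could be required at these ages. This is an optional addition that carries an extra test.

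The cost of the main change is one clause in two places of the protocol, plus a pregnancy test and a contraception requirement for at most a few more patients. The SAP needs no change.
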